12.2 Planned Listings

Data/ Endpoint	Description
Subject Listing of Important Protocol Deviations	Listing of the Important Protocol Deviations with category and sub-category codes, and descriptions for each subject, grouped by site.
Subject Listing of Randomized Treatment Assignments	Listing of randomized treatment assignments for each subject grouped by stratification factors
Listing of Unique Manufacturing Lot Numbers	Listing of the unique Manufacturing Lot Numbers used in the study, grouped by treatment group (investigational product name and concentration).
Subject Listing of Manufacturing Lot Numbers	Listing of the subjects administered each Manufacturing Lot Number grouped by treatment group (investigational product name and concentration).

12.3 Planned Figures

Data/ Endpoint	Description
Cumulative Distribution Function of IP Discontinuation <<Full Analysis Set>>	Cumulative distribution of time to IP discontinuation over time by randomized treatment group with reasons for ending IP noted.
Time to First RBC Transfusion <<Full Analysis Set>>	Time to first RBC transfusion by treatment group using on-treatment approach. Repeat with all randomized subjects using on-study approach.
Time to First RBC Transfusion or Ending Investigational Product due to Lack of Efficacy <<Full Analysis Set>>	Time to first RBC transfusion or ending IP due to lack of efficacy using on-treatment approach
[Hemoglobin] Over Time <<Full Analysis Set>>	Mean \pm SE [hemoglobin] over time. Repeat for all other laboratory parameters, SBP and DBP
Change from Baseline [Hemoglobin] Over Time <<Full Analysis Set>>	Mean \pm SE change from baseline [hemoglobin] over time. Repeat for all other laboratory parameters, SBP and DBP
Hemoglobin Rate of Change Over Time <<Full Analysis Set>>	Mean \pm SE hemoglobin rate of change over time.
Hemoglobin Variability Over Time <<Full Analysis Set>>	Mean \pm SE hemoglobin variability over time.
Darbepoetin alfa Dose Over Time <<Full Analysis Set>>	Median (IQR) darbepoetin alfa dose over time.
Darbepoetin alfa Weight-adjusted Dose Over Time <<Full Analysis Set>>	Median (IQR) darbepoetin alfa weight-adjusted dose over time.
[Hemoglobin] Over Time by Initial Hb Response <<Initial Hb Response Analysis Set>>	Mean \pm SE hemoglobin over time by initial Hb response and treatment group.

Darbepoetin alfa Dose Over Time <<Initial Hb Response Analysis Set>>	Median (IQR) darbepoetin alfa dose over time by initial Hb response and treatment group.
Darbepoetin alfa Weight-adjusted Dose Over Time <<Initial Hb Response Analysis Set>>	Median (IQR) darbepoetin alfa weight-adjusted dose over time by initial Hb response and treatment group.
Time to First RBC Transfusion <<Initial Hb Response Analysis Set>>	Time to first RBC transfusion by initial Hb response and treatment group using on-treatment approach.
Time to First <Major Clinical Event> - <<Full Analysis Set>>	Kaplan-Meier curves of time to first <major clinical event> using on-treatment approach. Major clinical events include composite of all-cause mortality and the occurrence of major cardiovascular events (stroke, myocardial infarction, and decompensated heart failure), composite of all-cause mortality, stroke or myocardial infarction, ie, major adverse cardiovascular events (MACE), all-cause mortality, cardiovascular mortality, stroke, myocardial infarction, decompensated heart failure, thromboembolic events, and vascular access thrombosis.
Time to First <Major Clinical Event> - <<All Randomized Subjects>>	Kaplan-Meier curves of time to first <major clinical event> using on-study approach. Major clinical events include composite of all-cause mortality and the occurrence of major cardiovascular events (stroke, myocardial infarction, and decompensated heart failure), composite of all-cause mortality, stroke or myocardial infarction, ie, major adverse cardiovascular events (MACE), all-cause mortality, cardiovascular mortality, stroke, myocardial infarction, decompensated heart failure, thromboembolic events, and vascular access thrombosis.

14. DATA NOT COVERED BY THIS PLAN

Currently there are no pre-planned analyses for the biomarker objective.

15. APPENDICES

Appendix A. Analytical Study Week Assignments

Selected endpoints will be summarized by scheduled study visits. Since the actual visits may not exactly coincide with their scheduled visit day, the actual visit day is mapped to the study visit generally by non-overlapping consecutive intervals covering the entire time continuum, with scheduled visit time being the center of each interval.

Such assignments will be based on the scheduled visits specified in the protocol. If there are more than 1 measurement taken during the specific study window, the measurement at that specific scheduled visit will be defined as the measurement taken closest to the planned visit day during that visit window. If 2 measurements are equidistant from the scheduled visit, then the earlier measurement will be chosen. If there are multiple values available on that same day, then the last record will be used.

- Schedule visit in RAVE will be used as the time point the measurement is taken.
- Except for the visit coded as “SCR” (screening and screening 1), “UNSCHED”, “ET” and “EOS”, the analytical study day will be used.

Measurements are categorized into 4 different schedules based on scheduled of assessments in the protocol. Over time summary on endpoint of interests will be completed only at scheduled time points. Post-baseline measurements will be summarized according to the following:

- For protocol-specified study assessment which occurred every 4 weeks (Hb through point of care device, systolic BP, diastolic BP and pulse), the planned study day and corresponding analytical study days to the scheduled study visit assignments are listed below

Scheduled Visit	Planned Study day	Analytical Study Days
Week 1	1	1 ≤ Study days ≤ 14
Week 5	29	15 ≤ Study days ≤ 42
Week 9	57	43 ≤ Study days ≤ 70
Week 13	85	71 ≤ Study days ≤ 98
Week 17	113	99 ≤ Study days ≤ 126
Week 21	141	127 ≤ Study days ≤ 154
Week 25	169	155 ≤ Study days ≤ 182
Week 29	197	183 ≤ Study days ≤ 210
Week 33	225	211 ≤ Study days ≤ 238
Week 37	253	239 ≤ Study days ≤ 266
Week 41	281	267 ≤ Study days ≤ 294
Week 45	309	295 ≤ Study days ≤ 322

Scheduled Visit	Planned Study day	Analytical Study Days
Week 49	337	323 ≤ Study days ≤ 350
Week 53	365	351 ≤ Study days ≤ 378
Week 57	393	379 ≤ Study days ≤ 406
Week 61	421	407 ≤ Study days ≤ 434
Week 65	449	435 ≤ Study days ≤ 462
Week 69	477	463 ≤ Study days ≤ 490
Week 73	505	491 ≤ Study days ≤ 518
Week 77	533	519 ≤ Study days ≤ 546
Week 81	561	547 ≤ Study days ≤ 574
Week 85	589	575 ≤ Study days ≤ 602
Week 89	617	603 ≤ Study days ≤ 630
Week 93	645	631 ≤ Study days ≤ 658
Week 97	673	659 ≤ Study days ≤ 686
Week 101	701	687 ≤ Study days

- For protocol-specified study assessment occurred at Day 1, Weeks 5, 13 and every 12 weeks (CBC, TSAT, ferritin, iron, TIBC), the analytical windows are:

Scheduled Visit	Planned Study day	Analytical Study Days
Week 1	1	1 ≤ Study days ≤ 14
Week 5	29	15 ≤ Study days ≤ 57
Week 13	85	57 ≤ Study days ≤ 126
Week 25	169	127 ≤ Study days ≤ 210
Week 37	253	211 ≤ Study days ≤ 294
Week 49	337	295 ≤ Study days ≤ 378
Week 61	421	379 ≤ Study days ≤ 462
Week 73	505	463 ≤ Study days ≤ 546
Week 85	589	547 ≤ Study days ≤ 630
Week 97	673	631 ≤ Study days

- For protocol-specified study assessment occurred at Day 1, Week 25 and every 24 weeks afterwards (eGFR and serum creatinine), the analytical windows are:

[figure not shown]
Scheduled Visit	Planned Study day	Analytical Study Days
Week 1	1	1 ≤ Study days ≤ 85
Week 25	169	86 ≤ Study days ≤ 252
Week 49	337	253 ≤ Study days ≤ 420
Week 73	505	421 ≤ Study days ≤ 588
Week 97	673	589 ≤ Study days ≤ 686
Week 101	701	687 ≤ Study days

- For protocol-specified study assessment occurred at Day 1, Week 13 and every 12 weeks afterwards (Anti-HLA antibodies), the analytical windows are:

Scheduled Visit	Planned Study day	Analytical Study Days
Week 1	1	1 ≤ Study days ≤ 43
Week 13	85	44 ≤ Study days ≤ 126
Week 25	169	127 ≤ Study days ≤ 210
Week 37	253	211 ≤ Study days ≤ 294
Week 49	337	295 ≤ Study days ≤ 378
Week 61	421	379 ≤ Study days ≤ 462
Week 73	505	463 ≤ Study days ≤ 546
Week 85	589	547 ≤ Study days ≤ 630
Week 97	673	631 ≤ Study days

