7.1.7 End of Study Evaluations

Subjects will complete an EOS visit at week 101 within \pm 5 days of the target visit date or at early termination. The following procedures apply to the EOS visit:

- Physical examination
- Blood pressure and pulse
- Weight
- Concomitant medications (as specified in [Section 7.2.9](#))
- RBC transfusions, as well as transfusions of other blood-derived products

- Endpoint data for adjudication
- Hospitalizations, including observational stays, and emergency department visits
- Adverse event and serious adverse event assessment
- eGFR, serum creatinine
- Hb, using the **modified** Hb POC device
- Blood samples for biomarkers
- Anti-erythropoietic protein antibodies
- Anti-HLA antibodies

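### The SAP's anti-HLA window table has no Week 101 row, so the end-of-study sample is either displaced by the Week 97 sample or has no row of its own

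*SAP*

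**What the plan says.** Protocol 7.1.3 takes an anti-HLA sample on Day 1. Section 7.1.4.1 repeats it every 12 weeks, with routine visits running to Week 97. The list for the EOS visit in 7.1.7 (Week 101, or early termination) again contains "Anti-HLA antibodies", and the Schedule of Assessments agrees. Both visits have a window of ± 5 days.

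SAP Appendix A assigns measurements to visits. Its general rule is that "the actual visit day is mapped to the study visit generally by non-overlapping consecutive intervals covering the entire time continuum". If a window holds several values, "the measurement at that specific scheduled visit will be defined as the measurement taken closest to the planned visit day during that visit window". The anti-HLA table, introduced by "For protocol-specified study assessment occurred at Day 1, Week 13 and every 12 weeks afterwards (Anti-HLA antibodies), the analytical windows are", has rows for Week 1 and for Weeks 13 to 97. The Week 97 row starts at Day 631 and is open-ended.

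Two other tables in the appendix cover measures that are also taken at EOS: the four-weekly table (point-of-care Hb, blood pressure, pulse) and the eGFR/creatinine table. Both close Week 97 at Day 686 and have a Week 101 row from Day 687.

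Two consecutive bullets deal with visit codes. One takes the visit recorded in RAVE as the time point. The next sets screening, unscheduled, ET and EOS codes apart in relation to the analytical study day, without making clear which side of the exception they fall on.

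In the CBC and iron table, Week 5 is "15 ≤ Study days ≤ 57" and Week 13 is "57 ≤ Study days ≤ 126".

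**The concern.** Allosensitization over time is an exploratory objective in both documents. SAP 10.5.3 plans anti-HLA summaries over time on both the on-treatment and on-study approaches, and again by transfusion subgroup. The EOS sample is a completer's last observation, and a by-visit table without it stops 28 days short of the follow-up that was collected.

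The subgroup tables add a mismatch. Under SAP 6.3 the on-study transfusion subgroup counts transfusions up to the end-of-study date. A transfusion between Weeks 97 and 101 can therefore move a subject to another subgroup, while the only scheduled antibody sample after that transfusion is left out of the same table.

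The omission looks like a slip. CBC and iron tests are not on the EOS list, and their table properly ends with an open Week 97 row. The anti-HLA table ends in the same way, although anti-HLA is drawn at EOS. Of the measures named in the four tables, it is the only one with an EOS draw and no EOS row.

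**Working it through.** **Inputs.** Planned days are 1 + 7 × (week − 1), as in Appendix A. Week 97 is 1 + 7 × 96 = Day 673 and Week 101 is 1 + 7 × 100 = Day 701. With ± 5 days (Protocol 7.1.4.1 and 7.1.7), Week 97 samples fall on Days 668–678 and EOS samples on Days 696–706.

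**Scheduled samples.** Day 1 (1), Weeks 13, 25, 37, 49, 61, 73, 85 and 97 (8), and Week 101 (1) make 10.

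**The plan's own split.** The midpoint of Days 673 and 701 is (673 + 701)/2 = 687. This reproduces the 686/687 boundary in the four-weekly and eGFR tables.

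**Reading A: EOS mapped by study day.** Days 696–706 all satisfy the anti-HLA Week 97 condition (Day 631 onward), so both samples compete for one row.

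| Sample | Days | Distance from Day 673 |
|---|---|---|
| Week 97, in window | 668–678 | 0 to 5 |
| EOS, in window | 696–706 | 696 − 673 = 23 to 706 − 673 = 33 |

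Of the 11 × 11 = 121 possible day pairs, the EOS sample is nearer in none. With no Week 97 sample, the EOS sample is alone in the window and is reported under Week 97.

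**Reading B: EOS exempt from study-day mapping.** The sample keeps its EOS code, but the anti-HLA table has no Week 101 or EOS row to receive it. The SAP does not say how it would be shown.

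**Which tables are affected.** For a completer last dosed at Week 97, the on-treatment period would run to Day 673 + 84 = 757, so it is cut at the EOS date. The EOS sample therefore lies inside both the on-treatment and the on-study periods.

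**After the fix.** With Week 97 ending at Day 686 and Week 101 starting at Day 687, Days 668–678 map to Week 97 and Days 696–706 to Week 101. Both samples are kept.

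**Day 57.** The midpoint of Days 29 and 85 is (29 + 85)/2 = 57, and it is listed in both windows. Testing every boundary in the four tables finds no other overlap and no gap. All other midpoints in the CBC and iron table go to the later window, so Day 56 is the consistent end for Week 5.

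**The case against.** A reader might infer that EOS anti-HLA results are never summarized. The documents do not support that. The Week 97 window is open-ended, so an EOS sample is used when the Week 97 sample is missing, though under the wrong visit label. Displacement also depends on Reading A. The bullet on visit codes can be read as exempting EOS, and because Week 101 is a scheduled protocol visit, a programmer could reasonably add it. That objection stands as far as it goes: what is established is a missing row and an unclear rule, and neither reading yields a specified Week 101 summary. The Week 101 rows elsewhere, defined by study day, suggest that Reading A was intended, but they do not settle it.

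A reader might also infer that a Day 57 blood count would be counted twice. In the ordinary case it would not. Day 57 is 28 days from both planned visits (57 − 29 and 85 − 57), so an in-window Week 5 or Week 13 sample, at most 5 days away, is preferred. With both present, the Day 57 value is used in neither window; with one missing, it is used once. Double use needs both to be missing and an off-schedule central sample on that exact day, and no CBC or iron test is scheduled at Week 9. Unscheduled visits also fall under the ambiguous bullet. The tie rule would not help in that rare case, because it covers two values for one visit: "If 2 measurements are equidistant from the scheduled visit, then the earlier measurement will be chosen". Hb endpoints use the point-of-care device and are untouched.

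Finally, one might object that a single sample 28 days after the previous one, for an exploratory endpoint, hardly matters. That limits the importance of the point; it does not justify dropping a sample that the protocol collects.

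**Conclusion.** The point holds in this limited form. The anti-HLA table has no Week 101 row although the protocol draws a sample then. Under study-day mapping, the EOS result is lost from the by-visit summaries for every subject with an in-window Week 97 sample, the usual case for completers. Under the other reading, its handling is unspecified.

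The size is one of 10 scheduled samples per such subject, covering the last 28 of 700 days (4%). As an illustration only, take the plan's 20% drop-out allowance as the share without both samples: 375 × 0.8 = 300 results per group would be set aside. The documents do not say how many subjects will have both samples, so the true number could lie anywhere from 0 to 375 per group.

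The effect is confined to a descriptive exploratory endpoint. The primary and secondary endpoints and the adjudicated clinical events are unaffected. The Day 57 overlap is a one-digit slip and adds no weight.

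**What to change.** In SAP Appendix A:

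- Change the last anti-HLA row to `Week 97: 631 ≤ Study days ≤ 686` and add `Week 101 (planned Day 701): 687 ≤ Study days`, matching the four-weekly and eGFR tables.
- Reword the bullet on visit codes to say that ET and EOS samples are mapped by study day. This also gives early-termination samples a defined place. Where a routine sample in the same window is nearer the planned day, the usual rule will still prefer it.
- As a tidy-up, end the CBC and iron Week 5 window at Day 56, so that "generally by non-overlapping consecutive intervals covering the entire time continuum" is true of that table as well.

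The cost is a few lines of SAP text and one more visit in the anti-HLA tables. No new sampling is needed. Under Protocol 7.3.2 the samples are stored and measured only after the study is complete, so the change should be made before those results are available.

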Appendix B. Code Fragments

CCI

CCI

Appendix C. Concomitant Medications

Concomitant medications collected will be summarized by the following categories using the ATC codes and concomitant medication preferred term (CMPREF) based on the most updated version of WHODrug available prior to database lock.

Category	sub-categories
Anti-hypertensive	ACEi and/or ARB
	Renin inhibitor
	Antiadrenergic, peripheral or centrally acting
	Beta blockers (including Alpha/beta blockers)
	Arterial smooth muscle vasodilator
	Calcium channel blockers
	Diuretics
	Other anti-hypertensives
Statin or other lipid lowering agents	Statin
	Other lipid lowering agents
Drugs used in diabetes	Insulin
	Sulfonamides
	Biguanides
	Thiazolidinediones
	Other anti-diabetic agents
Anti-inflammatory agents	Systemic corticosteroids
	NSAIDS
	Other anti-inflammatory
Aspirin or other antiplatelet agents	Aspirin
	Other antiplatelet agents
Anticoagulant	Vitamin K antagonists (Coumadin)
	Direct thrombin inhibitors
	Other anticoagulant
Erythropoiesis stimulating agent	Darbepoetin alfa
	Epoetin alfa
	Other erythropoiesis stimulating agent
Iron medications	Iron medications – intramuscular
	Iron medications – intravenous
	Iron medications – oral
